3.1.2 Run-in Phase (Month 0)

The study will be broken down into three discrete phases: (1) *Run-in* (2) *Experiment*, and (3) *Observation* (Figure 2). During the *Run-in* phase, every caregiver-child dyad will have access to the inhaler sensor app and will receive electronic ICS use monitoring. ICS use will be monitored using an electronic sensor that affixes to their ICS inhaler and will remain through the study *Observation* phase. Participants will be sent 4 text messages, each designed to elicit a response from the caregiver about the study technology or the study itself. (See Appendix 1 for content of the Run-in text messages) Participants for whom any inhaler use data is transmitted to the study platform within the first 2 weeks of the Run-in Phase AND reply to one or more of the 4 text messages sent from the study platform (“Responders”) will be randomized into one of three arms at the end of the Run-in phase. (see section 4.10 for details on procedures for “Non-responders”) The second two weeks of the Run-in Phase is designed to provide baseline adherence data.

[figure not shown]

Figure 2: Study schema for proposed RCT

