4.16.2 Efficacy Analysis

We will assess the effectiveness of randomization by comparing the study arm balance on key demographic, clinical, and past health care utilization variables using analysis of variance (ANOVA) and t-tests or the nonparametric equivalent for continuous variables and chi-square tests or Fisher exact tests for categorical variables.

Primary analysis: Our primary outcome will be monthly ICS adherence in months 0-3 (Experiment Phase). Secondary outcomes will include monthly ICS adherence in months 4-6 (Observation Phase), asthma control at the end of the Experiment and Observation period. Secondary outcomes will also include monthly ICS adherence in months 7-13 (follow up period) to assess feasibility and acceptability of longer durations of electronic monitoring. We will consider arcsine transformation on the ICS adherence outcomes as necessary. This technique is commonly used for proportion data. We will use generalized estimating equations (GEE) to adjust for within-subject correlations due to repeated measures for the study's primary and secondary monthly adherence outcomes. Models will include main effects for arm and time (month) and arm-by-month interaction terms to allow for differing ICS adherence over time between arms. The dependent variable of monthly ICS adherence will be defined as mean daily observed-to-prescribed ICS actuation proportion for each study month. Mean daily adherence proportion will be capped at 1, such that participants taking more than their prescribed daily dose cannot receive "extra credit" for doses taken on those days. All statistical tests will be 2-sided. A P-value <0.05 will be considered statistically significant.

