4.17 Sample Size and Power

Our analysis of pilot data demonstrates a 48% difference in ICS adherence when comparing a time interval with financial incentives (the same schema proposed in this study) to a time period without incentives. To ensure a power of 80% at a significance level of 0.05 to detect a more conservative 30% difference in average adherence between arms 1 and 3 in the *Experiment* phase (corresponding to 65% and 35%, respectively), 40 patients are required in each of these two arms. To ensure scientific rigor given the vulnerable nature of the population, we estimate ~20% loss to follow-up. Therefore, we will aim to enroll 50 participants in study arms 1 and 3 and 25 participants in arm 2, or 125 participants total, to achieve sufficient power to detect a difference between arms 1 and 3. The study is not to be powered to detect differences in arms 1 to 2 or 2 to 3 (hence the 2:1:2 randomization schema) or for health outcomes or cost offset; rather, it is intended to obtain preliminary estimates of marginal effects of the intervention components and effect sizes on utilization outcomes by comparing arm 1 to 2 and 2 to 3 to power a future multicenter study. Baseline data reveals that ~50% of children with at least 2 prior hospitalizations have a repeat ED visit or inpatient stay 6 months after the 2nd hospital discharge.

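### The primary GEE leaves out the run-in adherence that the trial collects as its baseline; this costs precision but does not affect validity or the stated power

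*Combined protocol and SAP*

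**What the plan says.** The primary analysis in 4.16.2 is a GEE on monthly ICS adherence. Its terms are given in one sentence: "Models will include main effects for arm and time (month) and arm-by-month interaction terms to allow for differing ICS adherence over time between arms". No other term is named for this model.

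On the run-in, 3.1.2 states: "The second two weeks of the Run-in Phase is designed to provide baseline adherence data". Section 3.2 repeats this and places the two baseline weeks before assignment to arms.

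No analysis in the document then uses that baseline as a covariate. The balance check in 4.16.2 covers demographic, clinical and past-utilization variables. The trajectory model covers the Experiment and Observation phases. The baseline factors listed for Aim 2 in 4.18 are demographic, clinical and utilization factors.

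The outcome window is stated in two ways. Section 4.16.2 puts the primary outcome in months 0-3. Sections 3.1.3, 4.4 and 4.14 put the Experiment phase in months 1-3, and 3.1.2 labels month 0 as the run-in.

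**The concern.** A pre-randomization measurement of the outcome itself is usually worth conditioning on, and here it is already being collected. Leaving it out widens the confidence interval for Arm 1 against Arm 3. Chance imbalance in prior adherence also goes uncorrected, in a trial of 125 whose randomization names no stratification factor (7.1.1).

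The Arm 2 comparisons matter too. Section 4.17 says they are not powered and are meant to supply preliminary estimates for a later multicenter trial. Precision is therefore what they have to deliver, and Arm 2 has only 25 children. Naming the covariate in advance also removes the temptation to choose it after seeing the data.

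**Working it through.** **Inputs from the documents.** Tests are two-sided at 0.05 (4.16.2: "All statistical tests will be 2-sided"). Power is 80%. The effect is 65% against 35%: "corresponding to 65% and 35%, respectively), 40 patients are required in each of these two arms" (4.17). Loss is about 20%, so 40 of 50 are analysed in Arms 1 and 3, and 25 × 0.8 = 20 in Arm 2.

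**Inputs not in the documents (assumed).** The correlation r between run-in and Experiment-phase adherence is taken as 0.3 to 0.7. The SD is taken as 0.30, and also as the value implied by the plan's own sample size. The formulas assume a linear model with equal variance at baseline and follow-up.

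**Step 1: reproduce the plan's figure.** With two proportions and unpooled variance, n = (1.960 + 0.842)² × (0.65×0.35 + 0.35×0.65) / 0.30² = 39.7, so 40 per arm. Then 40 / (1 − 0.20) = 50, and 50 + 25 + 50 = 125. Both figures are reproduced. The implied SD is √(0.455/2) = 0.477. No baseline adjustment enters this calculation.

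**Step 2: gain from a baseline covariate.** The variance is multiplied by 1 − r², and 40 per arm acts like 40/(1 − r²). Without adjustment at SD 0.30:

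- Arm 1 minus Arm 3: SE = 0.30 × √(2/40) = 0.067.
- Arm 1 minus Arm 2: SE = 0.30 × √(1/40 + 1/20) = 0.082.

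Each is then multiplied by √(1 − r²).

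| r | Variance factor, covariate | 40 acts like | SE Arm 1−3, points (SD 0.30) | SE Arm 1−2, points (SD 0.30) | Power Arm 1 vs 3 (SD 0.477) |
|---|---|---|---|---|---|
| none | 1.00 | 40 | 6.7 | 8.2 | 80.3% |
| 0.3 | 0.91 | 44 | 6.4 | 7.8 | 83.9% |
| 0.5 | 0.75 | 53 | 5.8 | 7.1 | 90.1% |
| 0.7 | 0.51 | 78 | 4.8 | 5.9 | 97.6% |

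The variance falls by 9%, 25% and 49%. At SD 0.30 the unadjusted Arm 1 against Arm 3 test has 0.30/0.067 = 4.5 standard errors, or about 99% power. The gain there is in interval width, not power.

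**Step 3: does the months 0-3 wording already use the baseline?** Suppose month 0 is an outcome row and the arm effect is free at month 0. The arm-by-month contrast against month 0 is then a change score, with variance factor 2(1 − r): 1.40, 1.00 and 0.60 at r = 0.3, 0.5 and 0.7. The covariate gives 0.91, 0.75 and 0.51. The difference is 2(1 − r) − (1 − r²) = (1 − r)², which is positive for every r below 1. Averaging the arm effect over months 0-3 instead would dilute a true 0.30 to 0.30 × 3/4 = 0.225.

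**Step 4: check on the three-month average.** Four monthly values per child were simulated with equal month-to-month correlation, SD 0.477 and 40 per arm. Standard errors for the months 1-3 difference, at correlations 0.3, 0.5 and 0.7, were:

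- unadjusted: 0.078, 0.087, 0.096
- change from month 0: 0.103, 0.088, 0.067
- covariate: 0.071, 0.069, 0.060

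The covariate was the most precise of the three throughout. On this parameterization the covariate's variance factor is about 0.83, 0.63 and 0.39, so the size depends on what r describes. The direction does not.

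**The case against.** The strongest reply is that nothing is broken. Omitting a baseline covariate in a randomized comparison leaves the estimate unbiased and the error rate intact, and the plan's 40 per arm meets its 80% target without one. That stands. A reader might infer from the omission that the primary test is biased or underpowered; the documents support neither reading.

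A second reply is that months 0-3, read literally, already bring run-in adherence into the model. This stands in part: at r = 0.7 a change contrast recovers most of the gain (0.60 against 0.51). At r = 0.3 it is worse than no adjustment (1.40), and it never matches the covariate. The literal reading also conflicts with 3.1.3, 4.4 and 4.14. Whether a month-0 value would include the set-up weeks 1-2 is not stated, so no weight is placed on that.

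A third reply is that a covariate list may have been dropped. The trajectory analysis in 4.16.2 and the hazard models in 4.18 refer back to covariates described earlier, and Aim 2 cites a section on covariates. No such list appears, and those references concern other models. The sentence on model terms is not worded as exclusive, but it names no baseline term.

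A reader might also infer that Arm 2 gains most. Proportionally it does not, because 1 − r² is the same for every contrast. Only the absolute fall in standard error is larger there.

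Finally, 7.1.1 mentions assignment both at enrollment and at the end of the run-in. Since 4.4 says participants do not learn their arm until the Experiment phase, weeks 3-4 should not reflect their knowledge of it.

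**Conclusion.** The point holds as a loss of efficiency. The primary model as written does not condition on the baseline the trial sets out to collect, and no other passage supplies it. For an assumed r of 0.3 to 0.7 and equal variances, adjustment would remove 9% to 49% of the variance of each arm contrast.

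What this buys for Arm 1 against Arm 3 depends on an SD the plan does not state. At the implied 0.477, power rises from about 80% to between 84% and 98%. At 0.30, power is already about 99% and only the interval narrows. The practical case therefore rests on interval width and on the small Arm 2 comparisons. The direction of the gain holds for any r above zero; its size cannot be read from the documents.

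**What to change.** In 4.16.2, state that:

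- the GEE outcome months are 1-3 (primary) and 4-6 (secondary), and month 0 is not an outcome;
- mean capped daily adherence in run-in weeks 3-4 is a covariate in both models;
- dyads without weeks 3-4 data stay in the analysis, by a missing indicator or mean imputation.

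The last item needs an explicit rule. Randomization requires transmitted data only in weeks 1-2 (3.1.2, 7.1.1), so the number lacking weeks 3-4 data is unknown. The text should also say whether a run-in day without transmitted data counts as zero use or as missing.

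The cost is a few sentences in the analysis section. The run-in data are already being collected, and the sample size need not change.

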4.15 Secondary Endpoints

Secondary endpoints will include the following:

- Adherence to ICS regimen in *Observation* interval (months 4-6)
- Adherence trajectory, as determined by group-based modeling of adherence patterns.
- Change in cACT score from first study visit to the second, third, fourth, and fifth study visits.
- Number of asthma-related emergency room visits, hospitalizations, and oral steroid courses between study conditions.
- Healthcare costs associated with emergency room visits, hospitalizations, and oral steroid courses between study conditions.
- Continued use of sensors in 7-13 month follow-up period (feasibility outcome)

Health system use outcomes will be assessed primarily using CHOP electronic health record data and, secondarily, via caregiver report to account for utilization that may have occurred outside of CHOP. ED visits, hospitalizations, and oral steroids courses will be characterized as asthma-specific using existing, validated asthma registry definitions that include asthma visit diagnoses, medication orders, and asthma pathway order set activation. Costs will be estimated using average insurance payments for asthma ED visits, hospitalizations, and oral steroid courses in addition to the costs of the intervention components (i.e. sensors, incentive value, and research staff support).

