4.18 Additional analyses

Hypothesis 1.2 Longer time intervals to next asthma-related ED or inpatient visit, and reduced healthcare use and costs, will be observed in Arm 1 compared to Arms 2 and 3 (and in Arm 2 compared to Arm 3).

Time to next asthma-related ED or inpatient visit from enrollment will be first modeled using the Kaplan-Meier plots. Study arms will be compared using log-rank tests and unadjusted Cox proportion hazards models. Adjusted hazard models will include the additional covariates described above and the Anderson-Gill method will be used to account for recurrent events. Total medical costs will be estimated for the 12 months following study enrollment, accounting for each asthma-related ED visit and hospitalization, as well as the expenses incurred with study participant incentives, sensors, and use of the WTH automated platform. We predict that intervention will reduce medical costs, thereby contributing to a *cost offset*. We will estimate potential savings in medical costs by calculating the difference in average total medical costs minus study-related expenses between study arms.

Aim 2. Assess proposed mechanisms by which intervention strategy influenced adherence trajectory.

Aim overview: The broad goal of this aim is to assess which participant and study characteristics are associated with different longitudinal adherence trajectories.

Characteristics to be examined include baseline factors (demographic, clinical, and prior health utilization factors), intervention strategy (study arm), and potentially modifiable behavioral characteristics. Of specific interest is how intervention strategy in the Experiment phase (study arm) influences child asthma self-efficacy, shared medication responsibility, and medication habit over time and how these characteristics vary with longitudinal ICS adherence trajectories. [Figure 4]

Hypothesis 2: Increases in (1) participant self-efficacy, (2) shared medication responsibility, and (3) habit score will partially mediate the relationship between study arm and sustained adherence trajectory.

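### Section 4.16.2 calls every P<0.05 significant, primary or secondary, and Hypothesis 1.2 predicts benefit for all three arm pairs, although 4.17 describes those comparisons as unpowered or preliminary

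*Combined protocol and SAP*

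**What the plan says.** The significance rule is in 4.16.2: "All statistical tests will be 2-sided. A P-value <0.05 will be considered statistically significant". It closes the paragraph headed as the primary analysis. The same paragraph lists the secondary outcomes (Observation-phase adherence, asthma control, months 7-13 adherence), and the rule is worded for all tests.

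Section 4.15 lists the secondary endpoints, among them "Number of asthma-related emergency room visits, hospitalizations, and oral steroid courses between study conditions". The secondary analysis in 4.16.2 adds an overall test of arm on trajectory group and selected arm contrasts by chi-square.

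Hypothesis 1.2 in 4.18 says that longer time to an ED or inpatient visit, and lower healthcare use and costs, "will be observed in Arm 1 compared to Arms 2 and 3 (and in Arm 2 compared to Arm 3". The arms are compared on event time by log-rank and Cox models.

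Section 4.17 powers one contrast, Arm 1 vs Arm 3 on Experiment-phase adherence. It disclaims power for the other two pairs, for health outcomes and for cost offset. Of the study it says "it is intended to obtain preliminary estimates of marginal effects of the intervention components and effect sizes on utilization outcomes", to be obtained by comparing Arm 1 with 2 and Arm 2 with 3 in order to power a later multicenter trial.

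**The concern.** Section 4.17 sets out one powered comparison and a set of estimates. Section 4.16.2 lets any of the other results be declared significant on the same terms as the primary, and 4.18 puts part of that set forward as a directional hypothesis for every arm pair. Nothing says which secondary result would count as a finding.

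Observation-phase adherence for Arm 1 vs 3 is the most exposed. It carries the question of lasting effect raised in 1.4 and 3.1.3. The disclaimers in 4.17 do not reach it, and it has no place in any testing order.

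At stake is what the trial may claim. Under the present wording, an isolated P<0.05 on utilization, asthma control, trajectory group or lasting adherence could be reported as a significant effect with no stated control of the error rate.

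**Working it through.** **The plan's own figure.** Section 4.17 sets the target: "To ensure a power of 80% at a significance level of 0.05 to detect a more conservative 30% difference in average adherence". The contrast is Arm 1 against Arm 3, and the assumed values and resulting size are given as "corresponding to 65% and 35%, respectively), 40 patients are required in each of these two arms". With unpooled variances,

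n = (1.960 + 0.842)² × (0.65×0.35 + 0.35×0.65) / 0.30² = 7.849 × 0.455 / 0.09 = 39.7, rounded up to 40.

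The allowance for attrition is stated as "we estimate ~20% loss to follow-up". Dividing, 40 / 0.80 = 50, which matches the enrolment target: "we will aim to enroll 50 participants in study arms 1 and 3 and 25 participants in arm 2, or 125 participants total". The figure reproduces by this formula (the pooled version gives 43). It uses the full two-sided 0.05 on one contrast and makes no allowance for any other test.

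**How many secondary outcomes.** From 4.15: Observation-phase adherence 1, trajectory group 1, cACT change at four visits 4, ED visits, hospitalizations and steroid courses 3, costs 1, continued sensor use 1. The total is 11. A count that leaves out trajectory and adds time to visit from 4.18 also gives 11, but it is a different set. Eleven is therefore an order of magnitude and not a fixed list of tests.

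**How many arm pairs.** Three pairs are explicit only in Hypothesis 1.2. Trajectory analysis uses Arms 1 and 2 against Arm 3, plus an overall test. No pairs are fixed for cACT or Observation-phase adherence.

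**One outcome, three pairs.** The statistic is z(i,j) = (mean i − mean j) / √(1/n_i + 1/n_j), with n = 50, 25, 50 and rejection at |z| > 1.96. The pairs share arms. The absolute correlation is 0.02/√(0.06×0.04) = 0.41 between 1 vs 2 and 1 vs 3 (and likewise between 2 vs 3 and 1 vs 3), and 0.04/0.06 = 0.67 between 1 vs 2 and 2 vs 3. Independent tests would give 1 − 0.95³ = 0.143. Simulation with the actual dependence gives 0.12. The result depends only on the 2:1:2 ratio, so equal loss across arms leaves it unchanged.

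**Eleven outcomes.** For independent tests on one pair, 1 − 0.95¹¹ = 0.43. The documents give no correlation between outcomes, so it was varied. The simulation used 200,000 replicates, no true difference between arms, equal correlation across outcomes and exact dependence among pairs. It gives the chance of at least one P<0.05:

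| Assumed correlation | 11 outcomes, Arm 1 vs 3 only | 11 outcomes, all three pairs |
|---|---|---|
| 0 | 0.43 | 0.76 |
| 0.3 | 0.37 | 0.69 |
| 0.5 | 0.30 | 0.59 |
| 0.7 | 0.22 | 0.45 |
| 0.9 | 0.13 | 0.29 |

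The last column is an upper bound: 11 × 3 = 33 tests, with 33 × 0.05 = 1.65 false positives expected.

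**The case against.** The strongest reply is that 4.17 already makes these analyses preliminary. It denies power for health outcomes and cost offset, which covers every outcome in Hypothesis 1.2 for all three pairs, and the hypothesis sits under additional analyses. A stated expectation of direction is not a decision rule, and the tests stay two-sided. This stands in part. But 4.17 speaks of power and purpose and does not say how a small P-value is to be read; 4.16.2 does. Low power does not reduce the false-positive rate, and 4.17 leaves Arm 1 vs 3 on Observation-phase adherence untouched.

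The second reply is that the test count is inflated, and this largely stands. Section 4.18 computes a cost difference without naming a test. No test is named for counts of visits or steroid courses. Section 4.16.2 places asthma control at two time points where 4.15 has four. Months 7-13 sensor use is labelled feasibility. Hypothesis 1.2 names tests only for event time, so its firm figure is 0.12 for three pairwise tests, or 0.05 if the log-rank test is a single three-arm comparison.

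A reader might infer that a false significant secondary result is likely. The documents do not support that. The chance passes one half only if all three pairs are tested on all 11 outcomes and correlation is moderate or low (0.59 at 0.5, 0.45 at 0.7). High correlation is plausible, since costs are built from the same visits and the cACT changes share a baseline. Nor do the documents say that significance claims would justify the later trial; 4.17 says estimates would be used to power it.

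**Conclusion.** The point holds as an inconsistency between the significance rule and the stated purpose, with a materially raised error rate. If no arm differs on any secondary outcome, the chance of at least one false significant result exceeds 0.05 in every multi-test setting examined, with 0.76 as a ceiling that the plan does not commit to. These sizes rest on assumed correlations and on a number of tests that the documents leave open.

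Two limits apply. The preliminary wording in 4.17 names Arm 1 vs 2 and Arm 2 vs 3; Arm 1 vs 3 on utilization and cost is covered only by the statement on power. The primary comparison and its sample size are not affected.

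**What to change.** In 4.16.2, replace the blanket rule with text to this effect:

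*The two-sided 0.05 significance rule applies to the primary comparison of Experiment-phase adherence between Arm 1 and Arm 3. All other secondary outcomes, including the trajectory tests, and all Arm 1 vs 2 and Arm 2 vs 3 comparisons are exploratory, are not adjusted for multiplicity, and are reported as estimates with 95% confidence intervals without claims of significance.*

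Optionally, insert one step between the two sentences: if and only if the primary comparison is significant, Arm 1 vs Arm 3 on Observation-phase adherence is tested at two-sided 0.05. This fixed sequence keeps the error rate over the two tests at 0.05. Without that step, Observation-phase adherence joins the exploratory set.

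In 4.18, reword Hypothesis 1.2 as an aim to estimate differences between arms in time to visit, healthcare use and costs, so that it agrees with 4.17.

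The cost is wording in two sections. Data, sample size and primary power do not change. The new text also names in 4.16.2 the contrast that 4.17 powers, which 4.16.2 does not do now. The sponsor gives up the right to call an isolated secondary or trajectory P<0.05 significant.
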